2.5.3 Design Rationale

The Phase 1b portion of this trial is designed to evaluate the safety and tolerability of escalating doses of KZR-616 when administered in addition to standard-of-care therapy for 13 weeks in patients with SLE. The Phase 2 portion of this trial is designed to evaluate the renal response, safety and tolerability of KZR-616 when administered for 24 weeks in addition to standard therapy in patients with active proliferative LN.

In the Phase 1b portion, at least 6 patients per dose level will be enrolled to receive SC injections of KZR-616. Patients eligible for this part of the study must demonstrate adequate SLE disease activity at screening, be serologically positive, and may currently be on at least one SLE therapy, including oral corticosteroid, immunosuppressant (MMF, AZA, MTX, or leflunomide), and/or antimalarial agents, with stable dosage regimen. As these patients continue to have active SLE disease despite standard of care therapy, they are in need of an effective new treatment. As this is the first multiple dose study of KZR-616 in SLE patients, dose administration and step-wise evaluation is carefully outlined, including a sentinel patient in each dose cohort. Decisions to escalate, expand, or decrease dose level or frequency following the first 4 weeks of treatment for at least 4 evaluable patients in a cohort will depend on review by a Data Monitoring Committee (DMC).

In the Phase 1b portion of the study, a 4-week period of dose-limiting toxicity (DLT) evaluation for at least 4 evaluable patients in each cohort is proposed. Based on nonclinical toxicity studies, tolerability after 4 weeks of treatment is predictive of safety through 13 weeks of treatment. In addition, exposure data in healthy subjects show that KZR-616 is rapidly cleared and has no accumulation. Weekly administration of KZR-616 could be interpreted as serial episodic dosing, with potential AEs and DLTs likely to occur upon initial exposure and with a reduced risk with repeat dosing based on the results of KZR-616-001. These safety data will support the use of the RP2D of KZR-616 in patients with active proliferative LN for which there is a potential to increase the depth or frequency of response to background standard therapy. In addition, these data will be used to inform the design of future studies in non-renal SLE.

In the Phase 2 portion of the study, a total of 20 patients with active proliferative Class III or IV LN (with or without Class V disease) will be enrolled to receive KZR-616 for a total of 24 weeks. Safety will be assessed throughout the 24 weeks of dose administration and the follow-up which will continue for 12 weeks post last dose. As this will be the first study of KZR-616 in patients with active proliferative LN, the data obtained are anticipated to be sufficient to enable design of future development studies for KZR-616.

Proof of activity is based on multiple disease response assessments in LN and SLE including evaluation for improvements in kidney function (changes in proteinuria and estimated glomerular filtration rate [eGFR]), changes in lupus disease assessments (Systemic Lupus Erythematosus Disease Activity Index 2000 [SLEDAI-2K] and, for the Phase 1b only, the British Isles Lupus Assessment Group [BILAG]), changes in serum biomarkers of disease (ANA, anti-dsDNA, anti-Smith, anti-ribonucleoprotein [anti-RNP], anti-Ro/La [anti-SSA/SSB], C3/C4, and 50% hemolytic complement [CH50]), and changes in daily corticosteroid use.

3 STUDY OBJECTIVES

3.1 Objectives (Phase 1b)

Primary Objective:

- To evaluate the safety and tolerability of KZR-616 when administered as a SC injection weekly for 13 weeks in adult patients with SLE with and without nephritis

Secondary Objectives:

- To select RP2Ds of KZR-616 when administered as a SC injection
- To characterize the PK of KZR-616

Exploratory Objectives:

- To explore the efficacy of KZR-616 in patients with SLE
- To explore the PD effects of KZR-616
- To explore biomarker, immunomodulatory, pharmacogenomic, and proteomic changes following KZR-616 treatment

3.2 Objectives (Phase 2)

Primary Objective:

- To assess the number of patients with a 50% reduction in UPCR after 24 weeks of weekly SC injections with KZR-616 when compared to baseline

Secondary Objectives:

- To evaluate the safety and tolerability of KZR-616 when administered as a SC injection weekly for 24 weeks
- To characterize the efficacy of KZR-616 on parameters of renal function when administered as a SC injection weekly for 24 weeks

Exploratory Objectives:

- To explore the PD effects of KZR-616
- To explore the efficacy of KZR-616 in clinical and serological indicators of SLE disease activity
- To explore biomarker, immunomodulatory, pharmacogenomic, and proteomic changes following KZR-616 treatment

[figure not shown]
4 STUDY DESIGN

4.1 Overall Study Design

This is a Phase 1b/2, multi-center study in which patients will receive KZR-616, administered as a SC injection weekly for 13 (Phase 1b) or 24 weeks (Phase 2).

As shown in Figure 1, the first portion of this trial is designed to evaluate the safety and tolerability of escalating doses of KZR-616 when administered in addition to standard-of-care therapy in patients with SLE (Phase 1b). The second portion of this trial is designed to evaluate the renal response, safety and tolerability of a single dose (60 mg) of KZR-616 when administered in addition to standard therapy in patients with active proliferative LN (Phase 2).

Figure 1 Study schematic for Phase 1b and Phase 2:

Abbreviations: DLT = dose limiting toxicity; SLE = Systemic Lupus Erythematosus

4.1.1 Phase 1b

The Phase 1b is an open-label multiple dose escalation study of KZR-616 to evaluate the safety, tolerability, and PK of KZR-616 in patients with SLE with and without nephritis.

KZR-616 will be administered as a SC injection weekly for up to 13 weeks. Safety assessments will begin after the patient provides written informed consent and continue through 12 weeks of follow-up visits.

4.1.1.1 Dose-Limiting Toxicities

A DLT is defined as any Grade 3 or higher study drug-related AE, according to National Cancer Institute Common Terminology Criteria for Adverse Events (NCI-CTCAE), Version 4.03, that occurs during the 4-week DLT evaluation period, with the following exceptions:

- Asymptomatic Grade 3 anemia, neutropenia, or thrombocytopenia returning to baseline or Grade ≤ 2 within 7 days without transfusion, growth factor support, or other active therapeutic intervention
- Grade 3 study drug administration-related reactions (e.g., systemic drug reaction), fatigue, anorexia, chills, nausea, diarrhea or vomiting lasting < 1 day

-
- Asymptomatic, isolated Grade 3 or higher changes in alkaline phosphatase, creatine phosphokinase, gamma-glutamyl transferase, lipase, or lymphocyte count

4.1.1.2 Dose Escalation Plan

For each dose level, at least 6 patients may be enrolled to assure the availability of at least 4 DLT-evaluable patients. Dose escalation guidelines are as follows:

- Each cohort within a dose level will include 1 sentinel patient who will receive KZR-616 at a selected dose on Day 1/Week 1
- If the sentinel patient does not experience a DLT, as defined below, within 48 hours and based on the clinical judgement of the investigator and medical monitor, the remaining patients in the cohort will be dosed
- If a DLT is experienced in the sentinel patient within 48 hours of injection, a second sentinel patient may be dosed with KZR-616 following a safety review by the DMC. If no DLT is observed after 48 hours in the second sentinel patient, the remainder of the cohort may be enrolled
- If 0 or 1 of 6, 0 or 1 of 5, or 0 of 4 patients (20% or less) in a cohort experience a DLT, the next dose level will be opened for enrollment after DMC review as below
- If 1 of 4 (25%) patients in a cohort, or 2 or more of 5 or 6 patients in a cohort experience a DLT, the maximum tolerated dose will have been exceeded and dose escalation will not continue

To evaluate tolerability, a minimum of 4 patients should receive KZR-616 at a specified dose level for at least 4 weeks prior to any decision by the DMC to dose escalate.

Patients who discontinue treatment prior to Week 5 will be considered DLT non-evaluable, unless they experience a DLT prior to Week 5. The DLT non-evaluable patients may be replaced until the necessary number of evaluable patients is achieved per dose level.

Escalation is planned to continue in 15 mg increments of KZR-616. Planned dose levels of KZR-616 to be explored are described in [Table 2](#) below. Other dose escalation increments may be proposed by the DMC based upon emerging safety, PK, PD, and/or efficacy data. Similarly, emerging data may prompt the DMC to recommend a different DLT evaluation period, or alteration of the dosing interval or duration. During the dose escalation period, and based on safety evaluation in patients, the DMC may also recommend that patients in subsequent dose cohorts receive prophylactic treatment (e.g., pulse corticosteroid and/or antihistamine) prior to initial doses to prevent AEs and/or intra-patient dose escalation to be employed with an initial tolerizing dose of 30 mg.

Table 2: KZR-616 Dose Levels

Dose of KZR-616 (mg)
45 mg
60 mg
75 mg

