 - If 0 or 1 of 6, 0 or 1 of 5, or 0 of 4 patients (20% or less) in a cohort experience a DLT, the next dose level will be opened for enrollment
 - If 1 of 4 (25%) of patients in a cohort, or 2 or more of 5 or 6 patients in a cohort experience a DLT, the maximum tolerated dose will have been exceeded and dose escalation will not continue

If dose escalation is halted due to excessive DLTs, dose escalation may resume if a review by the DMC of all cumulative data identifies a possible mitigating intervention(s) (e.g., corticosteroid pre-medication for injection site reaction). In such an instance, dose escalation may resume by enrolling at least 4 new patients in a new cohort at the same dose level at which escalation ceased, implementing the proposed intervention, and following the dose escalation guidelines above. If successful, any subsequent dose levels must incorporate the new intervention.

Dose escalation will occur after safety data for at least 4 patients, who received KZR-616 for at least 4 weeks, are reviewed and evaluated by the DMC.

Patients who discontinue treatment prior to Week 5 will be considered DLT non-evaluable, unless they experience a DLT prior to Week 5. The DLT non-evaluable patients may be replaced until the necessary number of evaluable patients is achieved per dose level.

Dose escalation increments other than 15 mg may be proposed by the DMC based upon emerging safety, PK, PD, and/or efficacy data. Similarly, emerging data may prompt the DMC to recommend a different safety evaluation period, or alteration of the dosing interval or duration.

[figure not shown]
Phase 1b will be completed upon fulfillment of enrollment of the highest dose level that is determined to be tolerated.

Phase 2:

Eligible patients with active proliferative LN who are treated with at least one immunosuppressive agent will receive KZR-616, 60 mg, weekly for 24 weeks.

Patients will be followed for 12 weeks after the last dose of study drug.

Study schematic for Phase 1b and Phase 2:

Abbreviations: DLT = dose limiting toxicity; SLE = Systemic Lupus Erythematosus

Treatment:

KZR-616 is a small molecule, covalent inhibitor of the immunoproteasome.

KZR-616 is supplied as both a frozen solution drug product and a refrigerated lyophilized drug product in single-use vials packaged in multi-vial cartons.

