- Prophylactic measures may be considered at the time of the first dose, or with subsequent doses if signs and/or symptoms consistent with a systemic drug reaction develop, including:
 - Fluid hydration, e.g., 30 mL/kg orally at least 48 hours prior to dosing; and/or 250 to 500 mL IV after dosing if symptoms are present
 - Antiemetics, acetaminophen, and antihistamines
 - Systemic corticosteroids (e.g., dexamethasone 4 mg or prednisone 25 mg) prior to subsequent doses. Use of systemic corticosteroids should be discussed in advance with the medical monitor as their use could confound efficacy assessments.

7.1.4 **Dose Modification Guidelines for KZR-616**

Dose Reductions

During Phase 1b and Phase 2, patients who experience a KZR-616-related AE, not otherwise subject to Individual Stopping Rules ([Section 9.1](#)), are permitted to undergo dose reduction of 15 mg for subsequent doses at the discretion of the investigator and with medical monitor and/or sponsor approval.

- Patients must continue to fulfill the Dosing Criteria in [Section 7.1](#) prior to each dose
- If the AE does not recur at the lower dose level for at least 2 doses, the original dose may be resumed with medical monitor and/or sponsor approval. If the AE then recurs, dose reduction may be attempted once more with medical monitor and/or sponsor approval. Only one attempt to resume the original dose is allowed per patient
- If the AE recurs at the reduced dose level with the same grade, it should be considered whether or not KZR-616 must be permanently discontinued

Otherwise, intra-patient dose escalations are not allowed.

Missed Doses

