Patients who do not fulfill Dosing Criteria ([Section 7.1](#)) may miss up to 2 consecutive doses in Phase 1b or Phase 2 or patients may miss up to 4 total doses in Phase 1b or up to 6 total doses in Phase 2 for any reason (e.g. AE, scheduling, emergency). Upon resumption of dosing, subsequent doses should be timed according to the original dosing schedule based on Day 1. Patients who cannot resume dosing within 2 weeks of the first missed dose or who miss more than 4 total doses in Phase 1b or 6 total doses in Phase 2 must permanently discontinue KZR-616 unless the doses in question were missed based on Study Stopping Rules ([Section 9.1](#)). If doses were missed due to implementation of Study Stopping Rules, then the patient should be discussed with the medical monitor to evaluate if KZR-616 should be discontinued. Any dose modifications should be discussed with the medical monitor and documented in the eCRF.

If study medication is permanently discontinued due to an AE, standard therapy and planned assessments (see Schedule of Assessments, [Section 14.1](#), Appendix A, and [Section 14.2](#), Appendix B, for Phase 1b and Phase 2, respectively) should continue for the protocol specified time period.

7.2 **Prior and Concomitant Medications**

A concomitant medication is any prescription or over-the-counter preparation, including vitamins and supplements. Any concomitant therapies must be recorded on the eCRF. Except as described below, prior and concomitant medication use will be recorded for the 60 days prior to screening until the last follow-up visit.

All prior SLE treatment (e.g., immunosuppressants, antimalarials, biologics) will be recorded, including corticosteroid use, from at least the previous 24 weeks prior to screening. When possible, all prior biologics should be recorded.

SLE Disease-Related Concomitant Medications

Patients should continue all concomitant medications related to SLE therapy throughout the study, as outlined in Inclusion/Exclusion Criteria (Section 5.2), this section (Section 7.2), and Table 3.

- All immunosuppressant therapies and antimalarial agents should be continued at a stable dose except when change is deemed necessary by the treating physician or clinical investigator, or if access is limited due to supply issues (see also Section 7.2.2).

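### The Phase 1b DLT-evaluability rule removes only patients who discontinue, so patients who miss or step down doses in the 4-week window stay in the denominator and can tilt the count toward escalation

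*Combined protocol and SAP*

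**What the plan says.** Section 4.1.1.2 (with the same rule in the synopsis) defines DLT non-evaluability by discontinuation alone: "Patients who discontinue treatment prior to Week 5 will be considered DLT non-evaluable, unless they experience a DLT prior to Week 5". It sets no minimum number of doses or dose intensity. Non-evaluable patients may be replaced.

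The count drives the decision. Escalation is allowed as follows: "If 0 or 1 of 6, 0 or 1 of 5, or 0 of 4 patients (20% or less) in a cohort". It stops as follows: "If 1 of 4 (25%) patients in a cohort, or 2 or more of 5 or 6 patients in a cohort experience a DLT". On enrolment, "at least 6 patients may be enrolled to assure the availability of at least 4 DLT-evaluable patients".

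Section 7.1.4 covers departures from the assigned dose in both phases. After a related AE that is not a stopping-rule event, patients "are permitted to undergo dose reduction of 15 mg for subsequent doses at the discretion of the investigator", with medical monitor and/or sponsor approval. Patients who fail the dosing criteria "may miss up to 2 consecutive doses in Phase 1b or Phase 2", with a Phase 1b limit of 4 missed doses in total. Neither provision excludes the DLT window.

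A separate sentence in Section 4.1.1.2 sets an exposure floor before any decision to escalate: "a minimum of 4 patients should receive KZR-616 at a specified dose level for at least 4 weeks". The synopsis version requires that data for "at least 4 patients, who received KZR-616 for at least 4 weeks, are reviewed and evaluated by the DMC", without mentioning the dose level.

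**The concern.** The 4/5/6 rule reads each cohort as a sample of patients tested at its dose level over four weeks. A patient with a DLT is always counted. A patient without one is counted unless treatment was discontinued. The only patients wrongly kept are therefore DLT-free patients with less exposure, and keeping them can only pull the proportion down.

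The under-exposure need not be random. Section 7.1.1 withholds doses for low counts, raised liver tests or a non-injection-site AE above Grade 2. Section 4.1.1.1 exempts some Grade 3 events from DLT status, such as asymptomatic cytopenias that recover within 7 days. A drug effect can thus interrupt dosing without being a DLT, and the patient then counts as DLT-free.

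At stake is whether the next planned level opens after 45 or 60 mg, and whether 75 mg is called tolerated.

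**Working it through.** **1. The plan's own fractions.** 1/4 = 25% (stop); 1/5 = 20% and 1/6 = 16.7% (escalate, 20% or less). These reproduce.

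**2. Least exposure without discontinuing.** Four weekly doses fall in the window (Days 1, 8, 15, 22). Day 1 is taken. Three consecutive misses force discontinuation, because dosing must resume within 2 weeks of the first missed dose. The minimum is therefore 2 of 4 doses.

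| Level | Planned in window | With two missed |
|---|---|---|
| 45 mg | 4 × 45 = 180 mg | 90 mg (50%) |
| 60 mg* | 30 + 3 × 60 = 210 mg | 30 + 60 = 90 mg (43%) |
| 75 mg* | 30 + 3 × 75 = 255 mg | 30 + 75 = 105 mg (41%) |

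*Assumes that the 30 mg step-up dose (Section 7.1) is the Week 1 dose; Phase 1b does not say so. A 15 mg reduction costs less: at 45 mg, 45 + 3 × 30 = 135 mg (75%); at 60 mg, 30 + 60 + 2 × 45 = 180 mg (86%).

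**3. Where the decision flips.** Take cohorts of up to 6 with at least 4 patients who either had a DLT or took the full window doses. Add DLT-free under-dosed patients and compare the rule with and without them.
- 0 DLTs: escalate either way.
- 1 DLT among 5 or 6 adequately dosed patients: escalate either way.
- 1 DLT among 4, plus 1 or 2 under-dosed: 1/5 or 1/6 as written (escalate), 1/4 without them (stop).
- 2 or more DLTs: stop either way.

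Only the third case flips, always from stop to escalate. It needs no assumed rate.

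**4. Does the exposure floor block the flip?** Section 9.1 holds study drug after a DLT until DMC review, so usually only three of the four have 4 weeks of dosing. The flip then needs one of three things: patients with missed doses count toward the floor, the DLT follows the fourth window dose, or dosing resumes after review. The floor sentence does not say how missed doses count. The synopsis version could be met by a dose-reduced patient. If step-up falls in Week 1, nobody at 60 or 75 mg can have a literal 4 weeks at the level inside the window. If four DLT-free patients did meet the floor at full dose, 1 DLT would already be 1/5 and nothing would flip.

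**5. Chance of escalating, 6 counted patients.** The documents give no DLT rate, so the true full-window risk p is assumed. Let s be the share of the cumulative hazard on dose 1, with the rest split equally over doses 2–4. A patient on 2 of 4 doses carries the fraction f = s + (1 − s)/3, so q = 1 − (1 − p)^f. Dose size is ignored. With four patients at p and two at q:

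P(at most 1 DLT) = (1−p)^4(1−q)^2 + 4p(1−p)^3(1−q)^2 + 2q(1−q)(1−p)^4.

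At p = 0.33:
- All six fully dosed: 0.67^6 + 6 × 0.33 × 0.67^5 = 0.090 + 0.267 = 0.358.
- s = 0.70: f = 0.80, q = 0.274; 0.106 + 0.289 = 0.396 (components rounded).
- s = 0.50: f = 0.667, q = 0.234; 0.423.
- s = 0.25 (constant hazard): f = 0.50, q = 0.181; 0.135 + 0.326 = 0.461.

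| p | All six full | s = 0.70 | s = 0.25 |
|---|---|---|---|
| 0.20 | 0.655 | 0.685 | 0.733 |
| 0.25 | 0.534 | 0.569 | 0.627 |
| 0.33 | 0.358 | 0.396 | 0.461 |
| 0.40 | 0.233 | 0.268 | 0.330 |

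If all the hazard were on dose 1 (s = 1), missed doses would change nothing.

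**The case against.** The best defence is that the plan has other protections. Escalation follows DMC review. Dose reductions need medical monitor and/or sponsor approval, dose modifications are recorded in the eCRF, and the medical monitor and a sponsor representative sit on the DMC. The 4-patient floor and the Section 9.1 hold after a DLT together block many versions of the flip. Most drug-related Grade 3 events in the window are themselves DLTs, so the toxicity-driven route is narrower than it first looks. All of this stands, and it limits the point. It does not remove it: nothing in the protocol tells the DMC to discount under-dosed patients, and the floor governs when to decide, not who is counted. The DMC charter, a separate document, may say more.

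Sections 2.5.1 and 2.5.3 expect reactions mainly at first exposure. That argues against constant hazard and makes the smaller figures more plausible. It also stands.

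A reader might infer three stronger things that the documents do not support:
- **That the plan declares under-dosed patients to be full-dose patients.** It does not. It simply fails to remove or flag them.
- **That a diluted count at 75 mg opens a further level.** Table 2 ends at 75 mg, so only the judgement that 75 mg is tolerated is exposed.
- **That the Phase 2 dose rests on this count.** Section 11.1.1 bases the recommended doses on safety parameters, PK, PD and DLTs together, and Sections 4.1.2 and 7.1 already set the Phase 2 level at 60 mg.

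**Conclusion.** The concern holds as a bias in a stated counting rule. Under-dosed, DLT-free patients stay in the denominator, and the effect runs only toward escalating or toward calling a level tolerated. The flip from 1/4 to 1/5 or 1/6 is exact, but it is confined to 1 DLT among 4 adequately dosed patients and depends on how the 4-week floor is read.

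With two of six patients on half the window doses, the rise in the chance of escalating across assumed risks of 20% to 40% is about 0.03 to 0.04 if 70% of the hazard is on dose 1, and about 0.08 to 0.10 under constant hazard. These figures rest on assumed DLT rates and hazard shapes, and they are conditional on that cohort make-up; how often it would arise cannot be judged from the documents. Severity: should fix, not a fatal flaw.

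**What to change.** Reconcile the synopsis and Sections 4.1.1.2, 7.1 and 7.1.4 on how missed, reduced and step-up doses count.

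1. Define a DLT-evaluable patient as one who either had a DLT in the window or completed a minimum number of the window's planned doses at the cohort's assigned regimen, including any step-up dose. The sponsor should state that minimum as a number.
2. Treat other patients as non-evaluable and replaceable, which the plan already allows.
3. Apply the 4/5/6 rule and the 4-patient floor to that same set, with identical wording in the synopsis and main text.
4. Show the DMC the count on that set, with missed and reduced doses listed beside it. For cohorts already completed, tabulate the count both ways.

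This changes who is counted, not how anyone is dosed. The cost is amendment wording, one extra column in the DMC output and possibly one replaced patient per cohort.
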